4.5. Study Design Rationale

4.5.1 Medical background

To date, there is no consensus on the standard of care for relapsed/recurrent glioblastoma. Prior to 2009, patients were offered older approved chemotherapies such as carmustine or lomustine, TMZ at different regimens, or even no further therapeutic intervention. In 2009, Avastin® (bevacizumab), the humanized monoclonal antibody to human VEGF, was approved by FDA as a single agent for adult patients with progressive disease following prior therapy on the basis of objective response rate, but has not (to date) demonstrated an effect on survival. Different regimens are commonly employed by clinicians in an effort to prolong life and/or provide other clinical benefits for patients with recurrent GBM but there is also no consensus in this clinical

^b Subject withdrew voluntarily from study

^c Early Termination due to only possibly related syncopal episode

setting. The prognosis for patients with relapsed/progressive disease remains very poor (median survival about 6 months).

A Phase 1 trial of SGT-53 monotherapy has been completed in patients with advanced solid tumors as described above. Tolerance of the agent was acceptable with no SAEs related to SGT-53 reported. No MTD was established. Ten doses of SGT-53 were administered over 5 weeks. The combination therapy of SGT-53 (10 doses) and docetaxel in the ongoing Phase 1b has been relatively well tolerated to date and responses have been observed. The dose for this Phase II trial will be 3.6 mg DNA per infusion. This is the highest dose administered in the Phase Ia trial.

This trial is a single arm study wherein SGT-53, at a dose of 3.6 mg DNA per infusion, will be administered by iv infusion. Patients will receive SGT-53 and Temozolomide in 28 day cycles. Patients who are responding to treatment (at least stable disease by RANO) may receive three additional cycle of SGT-53/Temozolomide therapy at investigator's discretion. The primary objective is to evaluate the 6 month PFS in patients treated with SGT-53 in combination with Temozolomide.

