If optional surgical resection will be performed, SGT-53 will be administered on day -3 and day -1 prior to surgery. Surgical resection of recurrent or progressive tumor is Day 0. 14-21 days post operatively and having recovered from the effects of surgery the patients will then start cyclical TMZ with SGT as described above. A maximum of 6 patients will be have this optional testing. Once the presence of exogenous wtp53 from SGT-53 is demonstrated in the resected tumor of 3 patients, the option for surgical resection for tumor analysis will no longer be offered.

4.6.1. Dose Selection:

In the Phase 1a study of SGT-53 as a single agent the nanocomplex was administered twice weekly for five consecutive weeks. No patient received more than 10 infusions in a single cycle. Two cycles of 10 infusions were administered to one patient.

In various clinical trials Temozolomide has been administered daily for 5 days in one 28 day period. To optimize effectiveness of the potential chemosensitization of SGT53, SGT53

treatment will be given three times prior to the start of temozolomide treatment. Pre-clinical studies have shown that the wtp53 tumor suppressor gene delivered by the SGT-53 nanoparticle functions to sensitize tumors to the chemotherapeutic agent, making them more responsive to the drug. Thus, it is critical that p53 be expressed when temozolomide is administered in order to have the benefit of the SGT-53. Using the proposed schedules, SGT-53 is being expressed at the start of temozolomide treatment. For patients who undergo optional surgical resection for tumor analysis, two doses of SGT-53 will be administered in the week prior to surgical resection of the tumor to demonstrate the presence of exogenous wtp53 in the tumor to validate SGT-53 crossing the BBB and targeting the tumor.

4.6.2. Treatment Duration:

Patients will receive a total of 3 cycles of TMZ in combination with SGT. Patients who are responding to treatment (at least stable disease by RANO) may receive three additional cycles of SGT-53/Temozolomide therapy at investigator's discretion. Alternatively, they may continue on Temozolomide alone at investigator's discretion.

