4.6.3.1 Primary Endpoints

PFS-6 using the RANO criteria (see Section 18.2) will be used as primary endpoints.

4.6.3.2.Secondary Endpoints

- Safety of the combination of SGT-53 and Temozolomide.
- PFS, OS
- Anti-tumor activity of the combination of SGT-53 and Temozolomide based upon the RANO criteria.
- The induction of apoptosis by SGT-53 in the tumor (optional procedure).
- Nanoparticle delivery (optional procedure)

4.6.4. Statistical hypothesis and sample size:

A total of 26 patients will be enrolled. A maximum of 6 patients will be enrolled to participate in the optional surgical resection for tumor analysis.

Patients who have received at least one dose of study drug will be considered evaluable for safety and toxicity endpoints. Patients who require a dose interruption or reduction during the initial cycle will remain evaluable for toxicities if the reduction or interruption is due to a DLT. Patients who do not complete one cycle of treatment but do not have a DLT may be replaced as described in more detail in Section 9.6.

The primary endpoint for the trial is PFS6. Progression-free survival will be defined as the time from study enrollment until the time of first occurrence of disease progression, relapse, or death due to disease.

The analysis of the biological correlate data in patients with surgical resection for tumor analysis has the overall goal of providing an increased understanding of the ability of SGT-53 to cross the Blood-brain Barrier and be delivered into tumor cells in the brain. As such, the objective of the tumor analysis is qualitative rather than quantitative. It should be noted that in the Phase I dose escalation trial of SGT-53, the presence of the exogenous wtp53 delivered by SGT-53 was found to be present in the tumors in a DNA dose dependent manner. Moreover, even the lowest dose of SGT-53 (0.6mg DNA/infusion) was not only found to be present in the tumors of the patients, but to have some anti-tumor effect. A DNA dose 6-fold higher (3.6mg DNA/infusion) is being used in this trial.

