• To evaluate the 6 month PFS in patients treated with SGT-53 in combination with Temozolomide.

Secondary:

- To assess safety of the combination of SGT-53 and Temozolomide.
- To evaluate progression free survival (PFS) and OS in patients in patients with recurrent or progressive glioblastoma or gliosarcoma treated with SGT-53 in combination with Temozolomide.
- To determine the anti-tumor activity of the combination of SGT-53 and Temozolomide based upon the RANO criteria in patients with recurrent or progressive GBM tumors.
- To assess nanoparticle delivery to tumor site by analysis of the presence of exogenous wt p53 in the tumor (optional procedure).
- To assess induction of apoptosis by SGT-53 in the tumor by flow cytometry or histology (optional procedure).

5. INVESTIGATIONAL PLAN

This is a prospective open label single arm Phase II study to assess the efficacy of nanoparticle delivery to tumor site of exogenous wt p53. This trial will also evaluate the safety, tolerability,

toxicity and efficacy of SGT-53 (given in combination with temozolomide) on PFS and OS in adult patients with recurrent Glioblastoma or gliosarcoma.

The study population (26 patients) will be registered through and treated at: MD Anderson Cancer Center, Texas, USA and China Medical University Hospital, Taichung, Taiwan, based on Inclusion/Exclusion Criteria (see Sections 6.1. and 6.2.)

Although an MTD for SGT-53 was not reached in the previous Phase Ia trial, the highest dose tested was 3.6mg of DNA. This is the dose of SGT-53 that will be employed in this trial. Below is the schedule of treatment:

Cycles 1-3 (1 Cycle is 28 days)

- Day 1: SGT infusion
- Day 4: SGT infusion
- Day 8: SGT infusion
- Days 9-13-: TMZ (150mg/m2 (cycle 1) increasing to 200mg/m2 (from cycle 2 onwards) as tolerated, provided the patient meets the criteria for non-hematological toxicity, ANC and platelet counts (see 9.7.2)
- Day 11: SGT infusion
- Day 15: SGT infusion
- Day 18: SGT infusion
- Days 19-28: No treatment

Cycles 4-6: Patients who are responding to treatment (at least stable disease by RANO) may receive three additional cycles of SGT-53/Temozolomide therapy at investigator's discretion. Alternatively, they may continue on Temozolomide alone at investigator's discretion.

When the Patient has Undergone Optional Surgical Resection For Tumor Analysis (4-6 patients only):

- SGT infusion on days -3 and -1
- Surgery on Day 0

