8.2. Efficacy Endpoints

To evaluate the PFS, 6 month PFS, OS in patients treated with SGT-53 in combination with Temozolomide. These parameters will be evaluated using RANO Response Criteria (Response Assessment in Neuro-Oncology). All patients who have measureable disease according to RANO, received at least one dose of SGT-53, and have had disease reevaluated will be included in the analyses of secondary endpoints.

Optional surgical resection for tumor analysis:

DNA PCR will be employed to determine the presence of the nanoparticle delivered exogenous wtp53 gene in the tumor sample obtained during surgical resection. A maximum of 6 patients will be have this optional testing. Detection of exogenous wtp53 in the tumors from at least 3 patients will be considered a positive outcome. If the presence of the exogenous wtp53 is detected in at least 3 of the first 4 tumors assessed, the option for surgical resection for tumor analysis will no longer be offered.

9. TREATMENT PLAN:

Cycles 1-3 (1 Cycle is 28 days)

- Day 1: SGT infusion
- Day 4: SGT infusion
- Day 8: SGT infusion
- Days 9-13: TMZ (150mg/m2 increasing to 200mg/m2 as tolerated, provided the patient meets the criteria for non-hematological toxicity, ANC and platelet counts)
- Day 11: SGT infusion
- Day 15: SGT infusion
- Day 18: SGT infusion
- Days 19-28: No treatment

In those patients who had a surgical resection, the 1st cycle of SGT-53 and TMZ will start 14-21 days post operatively and having recovered from the effects of surgery.

Cycles 4-6: Patients who are responding to treatment (at least stable disease by RANO) may receive three additional cycles of SGT-53/Temozolomide therapy at investigator's discretion. Alternatively, they may continue on Temozolomide alone at investigator's discretion.

Optional surgical resection for tumor analysis (Maximum of 6 Patients):

[figure not shown]
- SGT infusion on days -3 and -1
- Surgery on Day 0

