Patients will be monitored for response and disease progression with MRI brain scans every 2 cycles (8 weeks) and/or at the end of cycle 3, or earlier if progressive disease is suspected.

All patients who participate in this study will continue treatment with SGT-53 and TMZ after surgery. The following conditions should be satisfied before initiation of treatment with SGT:

- 1) They have recovered from the effects of surgery including adequate wound healing.
- 2) A brain MRI should be done no later than 72 hours in the immediate post-operative period to best assess the extent of residual measurable disease post-operatively.
- 3) The patient has followed the study requirements for birth control and pregnancy testing since the initial pre-operative doses of SGT and TMZ.
- 4) Post-operatively, patients must have adequate bone marrow function (absolute neutrophil count > 1,500/ μ L and platelet count of >100,000/ μ L), normal coagulation profile (PT/PTT), adequate liver function (SGPT, SGOT, and alkaline phosphatase <2.5 times upper limit of normal and bilirubin < 1.5 X upper limit of normal), adequate renal function (BUN or creatinine <1.5 times upper limit of institutional normal within 7 days prior to starting therapy.
- 5) The patient continues to meet all the eligibility criteria of the study outlined above.

10.2.2. Patients Not undergoing Surgical Resection:

Patients who have had surgery for recurrent glioblastoma will follow the guidelines listed above for patients with optional surgical resection for tumor analysis.

If no surgery has been performed, patients will start SGT-53 and TMZ on the morning of Cycle 1 Day 1 (C1D1). Each cycle will consist of 28 days. Patients will return to the clinic for twice weekly (every 3rd or 4th day) infusions of SGT-53 for three weeks (see treatment schedule diagram in section 9.1.1). Temozolomide will be taken daily by mouth daily on days 9-13 of each cycle. During week 4 of each cycle the patient will not

receive any treatments. Patients will return to the clinic on Day 29 (C2D1) and Day 57 (C3D1) for evaluation. If the drug has been well tolerated continued dosing will be permitted even if they appear to be progressing.

Patients will be monitored for response and disease progression with MRI brain scans every 2 cycles (8 weeks) and/or at the end of cycle 3 or earlier if progressive disease is suspected.

10.2.3. All Patients:

Evaluations done at each clinic visit are detailed in Section 18.1.

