10.4. Efficacy Assessments

10.4.1. Progression-Free Survival

The percentage of patients who are alive and progression-free clinically and radiologically 6 and 12 months after starting treatment will be evaluated using the Kaplan-Meier method. Progression is defined by any of the following using the RANO criteria:

- a) >25% increase in sum of the products of perpendicular diameters of enhancing lesions compared with the smallest tumor measurement obtained either at baseline (if no decrease) or best response, on stable or increasing doses of corticosteroids*.
- b) Significant increase in T2/FLAIR non-enhancing lesion on stable or increasing doses of corticosteroids compared with baseline scan or best response after initiation of therapy *not caused by co-morbid events (e.g. radiation therapy, demyelination, ischemic injury, infection, seizures, postoperative changes, or other treatment effects)
- c) Any new lesion

- d) Clear clinical deterioration not attributable to other causes apart from the tumor (e.g. seizures, medication adverse effects, complications of therapy, cerebrovascular events, infection, and so on) or changes in corticosteroid dose
- e) Failure to return for evaluation as a result of death or deteriorating condition
- f) Clear progression of non-measurable disease

Note: All measurable and non-measurable lesions must be assessed using the same techniques as at baseline.

*Stable doses of corticosteroids include patients not on corticosteroids.

10.4.2. Tumor response rate:

The percentage of patients with a complete or partial response 6 and 12 months after starting treatment will be evaluated using the RANO criteria:

Complete response (CR). Requires all of the following

- a) complete disappearance of all enhancing measurable and non-measurable disease sustained for at least 4 weeks
- b) no new lesions
- c) stable or improved non-enhancing (T2/FLAIR) lesions
- d) patients must be off corticosteroids (or on physiologic replacement doses only)
- e) stable or improved clinically

Note: Patients with non-measurable disease only cannot have a complete response; the best response possible is stable disease.

Partial response (PR). Requires all of the following:

- a) >50% decrease compared with baseline in the sum of products of perpendicular diameters of all measurable enhancing lesions sustained for at least 4 weeks
- b) No progression of non-measurable disease
- c) No new lesions

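### The tumor response rate in Section 10.4.2 reads as response status at months 6 and 12, so it may miss confirmed responses that end before month 6; best overall response should be defined.

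*Combined protocol and SAP*

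**What the plan says.** The secondary objective in the synopsis and Section 4.6.5 is "To determine the anti-tumor activity of the combination of SGT-53 and Temozolomide based upon the RANO criteria". The endpoint list in Section 4.6.3.2 names the same thing without a summary measure: "Anti-tumor activity of the combination of SGT-53 and Temozolomide based upon the RANO criteria".

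The only operational definition is in Section 10.4.2: "The percentage of patients with a complete or partial response 6 and 12 months after starting treatment will be evaluated using the RANO criteria". The same section requires a CR or PR to last; for PR the reduction must apply to "all measurable enhancing lesions sustained for at least 4 weeks", and CR carries the same 4-week condition.

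On imaging, Sections 10.2.1 and 10.2.2 say "Patients will be monitored for response and disease progression with MRI brain scans every 2 cycles (8 weeks"), and/or at the end of cycle 3. The calendars in Section 18.1 mark an MRI in days 23-28 of both cycle 2 and cycle 3. On treatment length, Section 4.6.2 says "Patients will receive a total of 3 cycles of TMZ in combination with SGT", with three further cycles optional.

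Section 8.2 sets who is analysed: patients with measurable disease who "received at least one dose of SGT-53, and have had disease reevaluated will be included in the analyses of secondary endpoints".

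**The concern.** A response rate is normally meant to show whether tumors shrink on treatment. Here a response can be reached and confirmed within the planned 12 weeks of treatment, but it is looked for only at months 6 and 12. A patient with PR at weeks 8 and 12 who progresses in month 5 would be recorded like a patient whose tumor never shrank.

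The setting makes such losses plausible. Section 4.5.1 says "The prognosis for patients with relapsed/progressive disease remains very poor (median survival about 6 months"), and Section 4.6.4 takes 15% as the historical PFS6. Because landmark responders are a subset of the patients who are progression-free at that time, the rate gives limited information beyond PFS6 on the anti-tumor activity objective. It also could not be set beside a response rate reported as best response.

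**Working it through.** **1. Which reading does the text support?** Section 10.4.1 gives the percentage alive and progression-free at 6 and 12 months after starting treatment, by Kaplan-Meier, which is a point-in-time rate. Section 10.4.2 follows with the same time phrase. Best response appears elsewhere only as a reference for measuring progression and in notes on non-measurable disease. No section defines best overall response, response at any time, or duration of response as an endpoint.

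**2. Can a response be confirmed and lost before month 6?** Planned treatment is 3 x 28 = 84 days. The calendar scans fall on study days 28 + 23 = 51 to 56 and 56 + 23 = 79 to 84, about weeks 8 and 12. They are nominally 28 days apart (range 79 - 56 = 23 to 84 - 51 = 33 days), so a 4-week response can be shown by about week 12. Month 6 is about week 26, which leaves some 14 weeks in which it can end.

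**3. Ordering of the rates.** Assume the same patients in each denominator, the same 4-week rule, and that a patient who has progressed is not counted again as a responder. Then:

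- response at month 6 <= best confirmed response, and strictly less if any confirmed response ends before month 6;
- response at month 6 <= PFS6, since a patient who has progressed or died is not in CR or PR.

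The same holds at month 12.

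**4. The plan's own figures.** The Simon design in Section 4.6.4 (stop at 2 or fewer of 18; negative at 6 or fewer of 26; P0 = 15%, P1 = 30%) reproduces. Exact type I error is 0.0826 against the stated 10%, and power is 0.7007 against the stated 70%. The expected numbers progression-free at month 6, if all 26 are enrolled, are:

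- at P0: 26 x 0.15 = 3.9
- at P1: 26 x 0.30 = 7.8

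These are means, not limits. By the exact binomial with n = 26, P(more than 4 progression-free) = 0.35 at 15%, and P(more than 8) = 0.37 at 30%.

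**5. Size of the loss.** The documents give no response rate or duration, so there is no figure to correct. An illustration, with all of its inputs assumed: response first seen at week 8 or 12, and exponential duration with median m months. The share of responders still in response at week L is 0.5^(((L - onset)/4.345)/m), with 4.345 weeks per month.

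| Median duration | Week 26 | Week 52 |
|---|---|---|
| 2 months | 24-33% | 3-4% |
| 3 months | 38-48% | 10-12% |
| 6 months | 62-69% | 31-35% |
| 12 months | 79-83% | 56-59% |

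For an assumed best confirmed response of 20% (26 x 0.20 = 5.2 patients), losing 25%, 50% or 75% of responses before month 6 would leave 15%, 10% or 5%.

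**The case against.** **The wording is not conclusive.** The notes in Section 10.4.2 speak of the best response possible, and a 4-week confirmation rule is usual for best response. The authors may have meant response by months 6 and 12. This stands as far as it goes: the landmark reading is the natural one, not the only one. The text should say which is meant, and the same edit settles it.

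**A reader might infer that no more than 4 to 8 of 26 patients could be counted at month 6, and that the remaining 70-85% are lost responders.** The documents do not support this. Those counts are expectations under P0 and P1 (working, step 4), and most patients who have progressed by month 6 may never have responded.

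**A reader might infer from the calendar that no scan exists at month 6 or 12.** The calendar covers only cycles 1-3, end of treatment and the 30-day visit. Section 10.2.4 adds end-of-treatment imaging, which after cycle 6 falls at 6 x 28 = 168 days, or week 24. Section 10.3 adds two-monthly MRI after a complete response, and for the first year after stopping for reasons other than complete response, progression or death. These scans may fall near both landmarks.

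**The net direction of bias is not fixed.** The Section 8.2 set leaves out patients who were not re-evaluated, which can raise the rate. For example, 4 responders are 4/26 = 15.4% of all patients but 4/20 = 20% if only 20 were re-evaluated (an assumed number). This stands, and it limits the ordering in step 3 to a common denominator.

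**The endpoint carries no decision.** Only PFS6 drives go/no-go, a missed early response works against the drug, and durable response at month 6 is a legitimate measure in its own right. This stands and lowers the weight of the point, but it is no reason to leave best response undefined.

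**Conclusion.** The point holds in limited form. Read naturally, Section 10.4.2 would not count a confirmed response that ends before month 6, and nothing else in the plan captures it. The rate may therefore miss early responses. To say that the reported rate will understate activity goes further than the documents allow: the loss depends on unstated response rates and durations, and the Section 8.2 denominator can push the other way.

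The conclusion rests on the landmark reading and, for the ordering of the rates, on a common denominator and confirmation rule. The primary endpoint, its two-stage rule and N = 26 are untouched. Severity is minor to moderate, for one secondary endpoint.

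**What to change.** In Section 10.4.2, define the tumor response rate as confirmed best overall RANO response: CR or PR sustained for at least 4 weeks, from Cycle 1 Day 1 until progression or new anti-tumor therapy, with an exact confidence interval. State how two scans less than 28 days apart are handled, since the calendar windows allow this.

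Use all treated patients as the denominator, and say that this replaces the Section 8.2 re-evaluated set for this endpoint, or report both. Keep response status at 6 and 12 months as supportive.

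The downside is that best response counts short-lived responses, so it should be shown beside the landmark rates. The cost is a wording change before analysis. It uses scans already planned and needs no extra visits or patients.
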